3.4 Treatment Assignment Procedures

3.4.1 Randomization Procedures

Randomization will be automated using a stratified block randomization scheme. Participants will be randomized following completion of the online baseline survey. We will stratify by cigarettes per day (>15 vs. <15) and frequency of smartphone use (daily vs. non-daily) since these factors might influence quitting smoking and program participation. Half will be randomized to each of the two study arms (control vs. experimental). Following randomization, participants will receive instructions on how to download and set up and access their assigned program on their smart phone.

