10.2 Sample Size Considerations

The primary analytic goals of this pilot study are to assess feasibility and to estimate the magnitude of intervention effects on study outcomes. The target sample size ($n = 60$) for this pilot is based on recommended guidelines for estimating effect sizes in behavioral treatment development research²² and not on our anticipated intervention effect size. By design, the pilot trial is not powered to evaluate efficacy or to test for statistically significant differences between intervention groups.

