All app comparisons will adjust for the assigned app, number of cigarettes smoked at baseline, and when applicable, the time of survey collection and interaction between follow-up time and assigned app. The latter interaction allows for results to be presented separately at one and 3-months post-baseline. If the outcome measure is collected at baseline and not identical across all participants at baseline, we will additionally adjust for the outcome measure at baseline. With this adjustment, the estimated average difference across study arms may also be interpreted as the average difference in change from baseline across arms. Depending on differences identified between arms at baseline that were not avoided despite randomization by chance, additional potential confounders may be adjusted for.

Outcomes collected via follow-up surveys are subject to missingness; however, per convention, missing data for smoking cessation outcomes will be imputed as smoking or failing to successfully quit smoking for at least 24 hours. For these outcomes, additional sensitivity analyses will be conducted using (1) complete cases only and (2) completed assessments using multiple imputation by chained equation²⁴ with 10 imputed data sets created with logistic regression imputation using Barnard-Rubin adjusted degrees of freedom²⁵. For all other outcomes, analyses will use complete cases only. Further sensitivity analyses may consider modification of the effect of intervention on the primary outcomes by gender.

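### Minor, free improvement: 10 imputed data sets leave avoidable seed-to-seed noise in the multiple-imputation sensitivity analysis of the cessation outcomes; 100 would remove about two thirds of it

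*Combined protocol and SAP*

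**What the plan says.** Section 10.3 (Final Statistical Analysis Plan) sets the main rule for the cessation outcomes: "missing data for smoking cessation outcomes will be imputed as smoking or failing to successfully quit smoking for at least 24 hours". It then adds two checks: "For these outcomes, additional sensitivity analyses will be conducted using (1) complete cases only and (2) completed assessments using multiple imputation by chained equation". The second check is run "with 10 imputed data sets created with logistic regression imputation using Barnard-Rubin adjusted degrees of freedom". The section gives no reason for 10, no seed and no limit on Monte Carlo error.

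The rule covers two of the three primary outcomes in Section 2.2.1: 7-day point prevalence abstinence at 3 months, and a quit attempt of at least 24 hours. Section 10.3 asks for a point estimate, a 95% confidence interval and a P-value for each comparison. It uses relative risks, with risk differences if events are too rare.

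Section 10.2 sets a target of 60 participants, and its aims are "to assess feasibility and to estimate the magnitude of intervention effects on study outcomes". It also states: "By design, the pilot trial is not powered to evaluate efficacy or to test for statistically significant differences between intervention groups". Section 3.4.1 allocates half to each arm.

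**The concern.** A multiple-imputation estimate averages over random draws, so it carries simulation error that shrinks only as the number of imputations grows. With about 30 people per arm and possibly few quitters, a handful of missing binary outcomes redrawn ten times can leave that error visible. Two analysts running the same code on the same data with different seeds could report noticeably different risk ratios and P-values.

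This is the only planned analysis that fills in a missing cessation outcome with anything other than failure. It is read by comparing its estimate with the main one, and that comparison is cleaner if it does not depend on the seed.

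**Working it through.** **The plan's own figure.** There is none to reproduce. Ten is a setting without a calculation, and the sample size of 60 rests on guidelines (Section 10.2).

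**Inputs from the documents.** 10 imputations, logistic imputation and Barnard-Rubin degrees of freedom (10.3); 60 participants (10.2); 1:1 allocation, so 30 per arm (3.4.1); Poisson model with robust standard errors, adjusted for baseline cigarettes (10.3).

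**Assumptions.** The documents give neither missingness nor event rates. Missingness was taken as 10%, 20% or 30% per arm. Observed events (control v experimental) were 1 v 4 to 2 v 8 for abstinence, and 8 v 13 or 10 v 15 for the quit attempt.

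**Step 1: size of the noise.** With M imputations and between-imputation variance B, the seed SD of the pooled log RR is √(B/M). If B is a share λ of the variance, the ratio to the standard error is about √(λ/M). With λ = 0.20, as found in simulation at 20% missing:

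- M = 10: √(0.20/10) = 0.14
- M = 100: √(0.20/100) = 0.045

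Whatever λ is, the reduction is 1 − 1/√10 = 68%. Across the simulated scenarios the ratio was about 10–17% at M = 10 and 3–5% at M = 100.

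**Step 2: the confidence interval.** Total variance is W + (1 + 1/M)B, where W is the within-imputation variance. With W = 0.80 and B = 0.20 it is 1.020 at M = 10 and 1.002 at M = 100. The standard errors differ by √(1.020/1.002) = 1.009, under 1%. Simulated median 95% intervals agree: 0.89–17.96 v 0.90–17.37 (2 v 8, 20% missing) and 0.45–29.6 v 0.45–28.6 (1 v 4, 10% missing).

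**Step 3: seed ranges on fixed data, 30 per arm, 20% missing.**

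| Outcome, events | Band over seeds | M = 10 | M = 100 |
|---|---|---|---|
| Abstinence, 2 v 8 | central 95% | RR 2.99–4.38, P 0.047–0.142 | RR 3.40–3.86, P 0.069–0.100 |
| Abstinence, 3 v 6 | central 95% | RR 1.58–2.17, P 0.23–0.48 | RR 1.77–1.95, P 0.30–0.38 |
| Abstinence, 2 v 6 | central 90% | RR 2.16–3.11, P 0.182–0.355 | RR 2.47–2.74, P 0.232–0.279 |
| Abstinence, 1 v 4 | central 90% | RR 2.99–4.92, P 0.161–0.338 | RR 3.53–4.11, P 0.209–0.258 |
| Quit attempt, 8 v 13 | central 90% | RR 1.47–1.74, P 0.126–0.305 | RR 1.56–1.64, P 0.177–0.228 |

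A repeat run, at the same counts and missingness, gave 3.1–4.6 (then 3.6–4.1) for 2 v 8, 1.65–2.39 (then 1.89–2.10) for 3 v 6, and 1.45–1.75 (then 1.55–1.64) for 8 v 13. The centre of a range depends on the simulated covariates: further 2 v 8 runs gave 2.6–3.9 and 3.3–4.7. The relative width is steadier: 4.38/2.99 = 1.46, 4.6/3.1 = 1.48, 2.17/1.58 = 1.37, 2.39/1.65 = 1.45.

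**Step 4: the quit attempt.** The smallest and largest central 90% ranges at M = 10 were 1.42–1.57 (10 v 15, 10% missing) and 1.46–1.77 (8 v 13, 30% missing). Their geometric midpoints are 1.49 and 1.61, so the movement is about ±5% (1.57/1.49) to ±10% (1.77/1.61).

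**Step 5: the risk-difference fallback.** For 1 v 4 with 10% missing, the risk difference ran over 0.119–0.160 at M = 10 and 0.133–0.145 at M = 100, with a standard error of 0.081. At M = 10 the seed SD is about (0.160 − 0.119)/(2 × 1.645) = 0.0125, or 15% of the standard error. The noise is not peculiar to the ratio scale.

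**Limits.** The imputation code approximates the package cited in the plan, and the 3-month outcome was analysed alone rather than in the two-time model. One run chaining both time points (1 v 4, 20% missing) gave 1.61–2.34 at M = 10 and 1.82–2.06 at M = 100.

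**The case against.** The case for leaving the plan alone is substantial, and most of it stands.

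- **Ten is defensible.** The method, number, model and degrees-of-freedom correction are all prespecified. With λ = 0.20 the relative efficiency is 1/(1 + 0.20/10) = 98%, and the pooling formula already carries the finite-M error into the interval. A reader might infer that the plan contains an error; it does not.
- **The check still works.** A reader might infer that an estimate that moves with the seed cannot test robustness. That is too strong. In the 2 v 8 case at 20% missing, missing-as-smoking gave about 3.8–3.9, complete cases 3.8–4.0, and the median imputation estimate 3.6–4.0. In the scenarios where it was checked, the ratio stayed above 1 for every seed. Complete cases is a second departure from the main rule, and it has no seed.
- **The largest ranges are not forecasts.** They come from sparse counts that the documents do not give, and the quit-attempt outcome is much steadier. Section 13's neighbour on recruitment and retention, Section 3.3, plans paid surveys and phone follow-up, so 20% or more missing cannot be presumed.
- **No decision hangs on the P-value.** The trial is declared unpowered. At 2 v 8 with 20% missing, only about 3–10% of 10-imputation seeds fell below 0.05 in one set of runs. In five other data sets where this was tracked, none did.

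What this does not answer is that a wide interval describes sampling uncertainty. It is no reason to keep avoidable variation in a reported estimate when removing it is nearly free.

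**Conclusion.** The point holds as a minor improvement. Ten imputations leave seed noise of about 10–17% of the standard error; 100 would leave about 3–5%. In risk-ratio terms this is visible for sparse abstinence counts and small for the quit attempt. The relative reduction of 68% follows from the formula alone. The risk-ratio ranges rest on the assumed counts and missingness, and on about 30 analysed per arm.

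The documents do not support reading this as a threat to the trial's conclusion. The main and complete-case analyses are unaffected, and the confidence interval is almost the same at either setting.

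**What to change.** In Section 10.3, change the number of imputed data sets from 10 to 100, and state that the random seed is fixed in advance and reported. Both parts are needed: fixing the seed alone would only freeze one arbitrary draw. Nothing else in the analysis has to change.

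The cost is one line of text and minutes of computing, with no added participants, visits or data. The one caveat is timing. Section 10.3 is titled as the final plan, and Section 5.4 describes a problem at 3-month follow-up in the past tense. If outcome data had been seen when the change is made, it should be declared as a change to the plan.

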2.2 Study Outcome Measures

As a pilot study, we do not have a single “primary outcome” of interest. Rather, we will examine a range of measures designed to inform our study objectives: assess the program’s feasibility (program engagement), acceptability (ratings of satisfaction and helpfulness), impact on cognitive mediators of change (self-efficacy, outcome expectations, and motivation) and impact on indicators of smoking behavior change (quit attempts, smoking reduction, and abstinence).

Outcomes will be used to assess whether the intervention warrants further refinement and whether a future randomized efficacy trial is warranted.

2.2.1 *Primary*

The primary outcomes of interest that will be explored are:

- Seven-day point prevalence abstinence (PPA) at 3-month follow up;
- Total program log-ins to the assigned program during the study period at 3 months post-enrollment;
- Self-reported presence of an intentional quit attempt lasting at least 24 hours since study enrollment by 3-month follow up.

2.2.2 *Secondary*

Key secondary outcomes that will be explored at the 1-month follow up only:

- Self-report of no smoking in the past 7 days.

Key secondary outcomes to be explored at both the 1 and 3-month follow up include:

- Overall satisfaction with assigned program;
- Helpfulness ratings for each personal experiment, as well as satisfaction ratings of the associated experimental program features;
- Self-report rating of motivation for quitting;
- Self-report ratings of self-efficacy for quitting smoking;

Secondary outcomes to be explored at the 3-month follow up only:

- Cumulative duration of assigned program utilization in minutes, based on automated program tracking data.

2.2.3 *Other Secondary & Exploratory Outcomes*

Given the exploratory nature of this pilot study we will also examine a range of other potential secondary outcomes to include: program duration days, number of days quit attempts were maintained, any quit attempt, NRT earned, NRT requested, NRT used, program component contact time, use of each intervention component, number of personal experiments completed, stage of change, utilization badges earned, change in smoking rate, and self-reported outcome expectations, motivation and self-efficacy for staying quit; self-efficacy for enacting related behavioral skills targeted in the experimental intervention.

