4.1 Description

Both arms will receive an mHealth intervention consisting of:

- Best-practice self-help guidance for quitting based on the US PHS' Clinical Practice Guidelines for treating nicotine dependence and best practice treatment recommendations (aka, **Quit Guide**)
- Ability to track how many cigarettes they smoke a day, calculate what they would save if they stopped smoking, read motivational testimonials from others, and take notes within the app on things they've learned.
- A **referral** to their local state tobacco quitline.
- The ability to earn and request a free 2-week starter kit of **nicotine replacement patches**.

Experimental participants will also receive:

- A series of 9 personal **experiments**, each designed to build motivation or teach the skills necessary to successfully cut-back or quit smoking. They may also receive reminder prompts to complete experiments which are not initiated or started.

-Proprietary Intervention Detail Redacted-

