10 STATISTICAL CONSIDERATIONS

10.1 Study Hypotheses

We hypothesize that by engaging in the experiments, ambivalent smokers in the intervention arm will have successive mastery experiences which will build their confidence and positive outcome expectations (i.e., belief that *I can control my smoking* or *I can quit when I am ready*) and, in turn, will better motivate them to change their smoking behavior, including making a successful quit attempt and, possibly, quitting smoking. We also expect that experimental participants will be more likely to use the provided nicotine replacement patches and tobacco quitline referral than are control participants.

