12.3 Informed Consent Process

Each person will provide consent to be screened for eligibility by phone. If screened eligible, they will provide verbal consent and be emailed a link to a study information sheet for their records. The study team may email a PDF as a back-up method if a participant is unable to open the study information sheet using the link.

Informed consent will include permission for contacting participants by push notification/mail/email/text to remind them of follow-up surveys and other study events and permission to collect all study data and track their use of the program. It will also include permission to order a 2-weekly supply of NRT patches from an online pharmacy and have it sent to participants' homes, for those participants meet the study requirements to receive the NRT and also specifically request for it to be mailed to them. (Note: receipt of the NRT is optional for participants.)

Participants are free to refuse to answer any survey questions or drop out of the study at any time. Participants will be instructed how to discontinue involvement in the intervention or drop out of the study as part of the consent process.

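### If 'NRT used' comes from the follow-up surveys, the complete-case rule drops non-responders who were never sent a kit, although their non-use of the provided patches is known

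*Combined protocol and SAP*

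**What the plan says.** Section 2.2.3 lists "NRT earned, NRT requested, NRT used" among the other secondary and exploratory outcomes. It names no data source for use and does not say whether use is limited to study patches. Section 10.1 is more specific: it expects that "experimental participants will be more likely to use the provided nicotine replacement patches".

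Section 4.1 gives both arms "The ability to earn and request a free 2-week starter kit of" patches. Under Section 12.3, participants give "permission to order a 2-weekly supply of NRT patches from an online pharmacy", and a kit goes out only "for those participants meet the study requirements to receive the NRT and also specifically request for it to be mailed to them".

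Section 10.3 has two missing-data rules. For cessation, "missing data for smoking cessation outcomes will be imputed as smoking or failing to successfully quit smoking for at least 24 hours", with complete-case and multiple-imputation sensitivity analyses. For everything else, "For all other outcomes, analyses will use complete cases only", with no sensitivity analysis of the missing data. The analysis population is all randomized participants who installed the app.

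**The concern.** Patch use is not a cessation outcome, so it falls under the second rule. If it is read from the surveys, an installer who returns no survey is missing. For an installer with no kit ordered, however, the answer about provided patches is already fixed by the study's own ordering. It needs no imputation model and no missing-at-random assumption.

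Dropping that person loses a known zero from a small sample. It can also bias the estimates. People who never engage enough to request a kit may also be less likely to return surveys; that is plausible, though the documents do not show it. In that case the complete cases over-represent recipients and overstate use, and a difference in response between arms feeds into the arm comparison. Section 10.2 makes estimating the magnitude of effects a main analytic goal, so the estimates matter even where tests do not.

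**Working it through.** **The plan's own figures.** There is nothing to reproduce. The target of 60 in Section 10.2 rests on pilot-study guidelines, not on a formula, and the documents state no kit-request, patch-use or survey-response rate. From the documents: 60 in total, half to each arm, hence about 30 per arm (all taken as installers). Every rate below is an assumption.

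**Notation, per arm.** r = share with a kit ordered; u = use among recipients; s1 and s0 = survey response in recipients and in the rest. Among recipients, use is taken as independent of response.

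- Full-sample use = r·u
- Complete-case use = r·u·s1 / [r·s1 + (1−r)·s0]
- Known non-users dropped = 30·(1−r)·(1−s0)
- Recipients with unknown use = 30·r·(1−s1)

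The complete-case value exceeds r·u exactly when s1 > s0, equals it when s1 = s0, and falls below it when s1 < s0.

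**Base case.** r = 40% experimental v 25% control, u = 75%. Full-sample use is 0.40 × 0.75 = 30.0% v 0.25 × 0.75 = 18.8%, RR 1.60.

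| Response: recipients / others | Complete-case use, exp. v control | RR | Known non-users dropped, both arms |
|---|---|---|---|
| 80% / 80% | 0.240/0.800 = 30.0% v 0.150/0.800 = 18.8% | 1.60 | 3.6 + 4.5 = 8.1 |
| 90% / 70% | 0.270/0.780 = 34.6% v 0.16875/0.750 = 22.5% | 1.54 | 5.4 + 6.75 = 12.15 |
| 95% / 60% | 0.285/0.740 = 38.5% v 0.178125/0.6875 = 25.9% | 1.49 | 7.2 + 9.0 = 16.2 |
| 90% / 75% exp., 60% control | 0.270/0.810 = 33.3% v 0.16875/0.675 = 25.0% | 1.33 | 4.5 + 9.0 = 13.5 |
| 75% / 90% | 0.225/0.840 = 26.8% v 0.140625/0.8625 = 16.3% | 1.64 | 1.8 + 2.25 = 4.05 |

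**No true difference.** With r = 30% in both arms, use is 22.5% in each. With recipients responding at 90% and others at 80% experimental v 60% control, complete cases give 0.2025/0.830 = 24.4% v 0.2025/0.690 = 29.3%, RR 0.83. Swapping the two response rates gives 29.3% v 24.4%, RR 1.20.

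**Keeping the known zeros (90% / 70% row).** Only 30 × 0.40 × 0.10 = 1.2 and 30 × 0.25 × 0.10 = 0.75 recipients remain unknown, about 2 of 60. Counting them first as non-users and then as users bounds use at 27.0% to 31.0% (0.27 to 0.27 + 0.04) v 16.9% to 19.4% (0.16875 to 0.16875 + 0.025).

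**A half-fix goes wrong.** Filling in the zeros but still dropping recipients without a survey gives 0.270/0.960 = 28.1% v 0.16875/0.975 = 17.3%, below the full-sample 30.0% v 18.8%.

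**The case against.** The strongest objection is that the rule does not literally order this error. A value derivable from records is not missing, and a complete-case analysis could keep it. The plan is silent on how 'NRT used' is derived, and Section 6 leaves procedures to a manual that is not part of the documents. Section 2.2.3 does not restrict the outcome to study patches, and Section 1.3.1 notes that patches can be bought over the counter. If any NRT counts, a person without a kit is not a known non-user. Section 12.3 is a consent permission and describes no order log.

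Part of this stands. The point is conditional on a survey source and applies only to provided patches. But app analytics can show that a kit was earned or requested, not that a patch was worn, so a survey is the natural source. The hypothesis in Section 10.1 concerns provided patches. A study that places the orders can be expected to know for whom it placed them. No text sets use to 'no' when no kit was ordered.

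A reader might infer that the plan inflates patch use or manufactures an arm difference. The documents do not support either. Inflation needs recipients to respond more often than others, and no response rate is given; Section 13.3 is silent on rates, while Section 3.3 describes payment per survey and phone follow-up, which should limit non-response. With the same response pattern in both arms, and recipients responding more, the RR in these examples moves toward 1. The larger shifts need an assumed arm difference of 15 or 20 points in response among those without a kit.

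The objection on weight also stands. With 9 v 5.6 users of 30, the standard error of the log RR is √(1/9 − 1/30 + 1/5.6 − 1/30) = 0.47, so the unadjusted 95% interval around 1.60 runs from about 0.63 to 4.0. A shift of 0.06 to 0.11 is small beside that. Kit requests can already be compared by arm without survey loss.

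**Conclusion.** The point holds in conditional form, as a minor one. If 'NRT used' is survey-based and concerns the provided patches, the complete-case rule discards values that the study already knows: about 12 to 16 of 60 when 30% to 40% of those without a kit do not respond, under the assumed request rates. That loss occurs whenever a non-responder was never sent a kit. Bias is a further possibility and its direction is open: use is overstated if recipients respond more, understated if they respond less, and unaffected if response is equal. In the illustrations the RR of 1.60 becomes 1.54 or 1.49 under a common response pattern, and a true RR of 1.00 becomes 0.83 or 1.20 when response differs by arm. These sizes rest wholly on assumed rates. The outcome is exploratory, and the pilot is not powered to test for differences.

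**What to change.** In Section 10.3:

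- Define the outcome as use of study-provided patches.
- Code 'no' for every installer with no kit ordered by the date of the given assessment (1 or 3 months), regardless of survey response.
- Treat as missing only recipients without a survey answer. Use multiple imputation, fitted among recipients, for the primary estimate. The method is already planned as a sensitivity analysis for cessation outcomes. With few recipients per arm (12 and 7.5 in the base case) the imputation model must be small. Do not drop these recipients.
- Report their number by arm, with bounds counting all of them as users and none as users.
- Keep complete case as a sensitivity analysis, and report use of any purchased NRT as a separate survey-based outcome.

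The cost is a few sentences in the analysis plan, a merge with the kit-order records and a little more analysis. No new data are needed.
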